## **3. OBJECTIVES AND OUTCOMES**

The HEALing Communities Study (HCS) will test the impact of the Communities That HEAL (CTH) intervention on opioid overdose deaths and associated outcomes in 67 highly affected communities in Kentucky, Massachusetts, New York, and Ohio. The goal is to reduce opioid overdose deaths by 40%.

The HCS is a multi-site, parallel arm, cluster randomized, wait-list controlled trial evaluating the impact of the CTH intervention compared with usual care in wait-list communities. The CTH is a community-engaged intervention that provides community-based communication campaigns along with a comprehensive, data-driven community response plan to deploy evidence-based practices across multiple sectors to reduce opioid-related overdose deaths and associated outcomes.

As described, the HCS refers to the communities randomized to implement the CTH intervention first as Wave 1 communities and those in the wait-list comparison arm as Wave 2 communities. Wave 1 communities will implement the CTH intervention for 30 months, during which time Wave 2 communities will provide usual care. At month 31, Wave 2 communities will begin to implement the CTH intervention.

The HCS has one primary hypothesis (H1) and three secondary hypotheses (H2, H3, H4). Compared with Wave 2 communities, we hypothesize that Wave 1 communities will accomplish the following:

- H1: Reduce opioid overdose deaths.
- H2: Increase naloxone distribution.
- H3: Expand use of buprenorphine for opioid use disorder.
- H4: Reduce high-risk opioid prescribing.

The primary analysis will compare Waves 1 and 2 during the 12-month period of July 2021 through June 2022. This comparison period begins 18 months after Wave 1 communities implement the CTH intervention and before Wave 2 communities implement the CTH intervention.

The primary outcome is the number of opioid overdose deaths. Key secondary outcomes include (1) the number of naloxone units distributed in the community, (2) the number of

individuals with opioid use disorder (OUD) who receive buprenorphine, and (3) incidents of high-risk opioid prescribing. The primary comparison of interest is between Wave 1 and Wave 2 communities during the 12-month parallel-arm period. The primary analysis will use an intention-to-treat design with the population, defined as any community randomized into the HCS.

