**ORCCA EBP Requirement 1: OEND in high-risk populations**

Opioid overdose victims die when they do not receive an antidote in time. In many cases, naloxone can completely reverse opioid overdoses. To implement ORCCA EBP Requirement 1, community action plans will need to include strategies that actively distribute naloxone and provide overdose prevention education to high-risk individuals and their social networks at high-risk venues. Optional strategies that can be included in the community action plan are OEND by referral, OEND by self-request, naloxone availability for immediate use in overdose hotspots, and capacity for first responder administration.

**ORCCA EBP Requirement 2: Effective delivery of MOUD, including agonist/partial agonist medication and outreach and delivery to high-risk populations**

Reducing opioid overdose fatalities and improving secondary study outcomes will require increasing the availability of MOUD. Improved access to evidence-based MOUD treatment, particularly agonist/partial agonist treatment, can significantly reduce the risk of overdose death. The most effective treatment for OUD is MOUD, including methadone maintenance, buprenorphine maintenance, and naltrexone. MOUD significantly reduces the likelihood of opioid overdose, human immunodeficiency virus transmission, and hepatitis C virus transmission. MOUD is also associated with increased employment rates, increased quality of life, decreased crime, and decreased utilization of high-cost health care services.

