## 8.2 Safety Assessments

As described in Section 2.3, the risks associated with the CTH intervention are minimal. The CTH intervention does not directly treat members of the communities. Rather, it assists the communities and their service venues in selecting evidence-based practices (EBPs) that the communities will implement, and which were previously demonstrated as safe and effective. Thus, safety outcomes are not the driving issue for our monitoring assessments, and we do not expect to find adverse impacts of the HCS intervention. However, recognizing that the study will

collect data on opioid-related mortality and morbidity, the HCS will monitor adverse events (AEs) and serious adverse events (SAEs). It is very unlikely that opioid-related overdose events will be directly associated with the study; nevertheless, Wave 1 and Wave 2 communities will be monitored, and monthly reports of AEs and SAEs will be prepared and reviewed as described below.

The primary outcome for the HCS is opioid-related overdose fatalities; however, accurate fatality data are not available in a timely manner (i.e., the data lag is 6 months or more). Therefore, monitoring of opioid-related overdose fatalities is not a feasible measure that is available rapidly and reliably. For the HCS, we will monitor emergency medical services (EMS) runs for suspected opioid-related overdoses where naloxone was administered. The four HCS Research Sites (RSs) already have access to EMS runs that could be requested monthly, with a 30–90-day lag after the end of each month. The HCS will estimate the rate of suspected opioid-related overdose events by month in a community with the rate being the number of events per 1,000 community members. In this manner, EMS runs provide the HCS with an early warning sign of an increase in opioid-related overdose events in HCS communities.

To determine if there is a situation where AEs or SAEs might be related to the HCS, we will employ a two-step AE/SAE review process (Figure 10). Step one involves distinguishing whether the observed AE or SAE from monthly monitoring reports is a “safety signal”. If it is, then we will proceed with step two which involves assessing if the AE or SAE is related to the HCS.

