## 8.3 Adverse Events

### 8.3.1 Definition of Adverse Events and Serious Adverse Events

The HCS will use EMS opioid-related overdose runs to monitor opioid-related overdose events as an AE and an SAE. These events provide important knowledge about the opioid crisis that the HCS should ethically investigate and report to the community coalitions involved, the National Institute on Drug Abuse (NIDA), the Substance Abuse and Mental Health Services Administration SAMHSA, the Institutional Review Board (IRB), and the Data and Safety Monitoring Board (DSMB). The HCS does not collect any data attributable to specific individuals who received services from the HCS intervention. Only aggregate data for an entire community will be available.

- AEs will be identified by the following criterion:
  - The opioid-related overdose rate for a single month increases **more than three standard deviations** above the moving average of the previous 3 months. For example, the rate in a community for April 2020 is more than three standard deviations greater than the average rate for January, February, and March 2020.
- SAEs will be identified by the following criterion:
  - The opioid-related overdose rate for a single month increases **more than four standard deviations** above the moving average of the previous 3 months. For example, the rate in a community for April 2020 is more than four standard deviations greater than the average rate for January, February, and March 2020.

The standard deviation will be determined as the rolling standard deviation calculated from the 12 months prior to the target month.

Opioid-related overdoses are expected events in the HCS communities because, to be eligible for being selected into the HCS, NIDA required communities to be highly affected by the opioid epidemic with minimum numbers and rates per 100,000 of opioid-related overdose fatalities in 2016.

We will follow a metric-based approach to help identify safety signals and evaluate relatedness to the HCS. Table 11 describes both the monthly and cross-month metrics that serve as triggers

for further analyses. If one of these events occurs, we will consider it a safety signal and will proceed with conducting a relatedness analysis. This analysis will help determine whether observed AE/SAEs are directly related to the HCS intervention and inform further action if necessary.

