2	Definition Name	Person-months in MOUD
3	Population	Medicaid
4	Data Sources	Medicaid administrative data
5	Other Available Data for Additional or State-Specific Analyses	All-payer claims in Massachusetts; OASAS in New York, Ohio can combine claims from Medicaid and OhioMHAS; BSAS in Massachusetts
6	Primary Outcome Measure	
Identify all individuals with an OUD diagnosis who received MOUD during the measurement period.
 
For each individual, calculate the number of person-months during the measurement period that the individual maintained continuous MOUD by (1) prescription MOUD, (2) office-administered MOUD, or (3) a combination of both. Continuous treatment is calculated based on days' supply and dosage, and an individual can have a gap of no more than 7 days' treatment to be considered in continual treatment.
 
Outcome measure at the HCS community level is the total number of person-months in continuous MOUD.

7	Population Size Adjustment	Number of member-months enrolled during the 12-month study period for full-benefit Medicaid enrollees, aged 18–64, who were identified as individuals with OUD

1	Definition Number	2.8.1
2	Definition Name	Number of emergency medical services (EMS) naloxone administration events
3	Population	An emergency-response patient-EMS encounter
4	Data Sources	EMS run data, typically collected by the state's board of EMS as part of national reporting to NEMSIS ( https://nemsis.org/technical-resources/ )

5	Other Available Data for Additional or State-Specific Analyses	N/A
6	Primary Outcome Measure	Number of EMS runs that involve naloxone administration
7	Population Size Adjustment	Mid-year population estimate

1	Definition Number	2.8.2
2	Definition Name	Number of EMS runs for opioid-related incidents/overdoses
3	Population	Any emergency-response patient-EMS encounter
4	Data Sources	EMS run data, typically collected by the state's board of EMS as part of national reporting to NEMSIS ( https://nemsis.org/technical-resources/ )
5	Other Available Data for Additional or State-Specific Analyses	N/A
6	Primary Outcome Measure	Number of EMS runs for opioid-related incidents or overdoses

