6.5 Harms

In the HCS main trial, emergency medical service (EMS) runs for suspected opioid-related OD, as defined by each research site, were monitored as a safety measure. The four HCS RSs already had access to EMS runs that could be requested at monthly frequency, with a 15-day lag after the end of each month. The HCS estimated the rate of suspected opioid-related OD deaths by month in a community as number of events per 1,000 community residents. In this manner, EMS runs provided the HCS main trial DSMB team with an early warning sign of an increase in the rate of opioid overdose deaths in HCS communities. A three-month moving average of the rate of opioid OD deaths was calculated using the EMS data. If a single month had an estimated rate that was more than three standard deviations above this moving average, then an adverse event (AE) was considered to have occurred. If a single month had an estimated rate that was more than four standard deviations above this moving average, then a serious adverse event (SAE) was considered to have occurred. The HCS also follows a metric-based approach to identify safety signals. If any of the following metrics are observed, a detailed review of the events will be conducted to evaluate their relatedness to the HCS. Monthly metrics are triggers observed in a single month across all communities: a) five AEs, b) two SAEs, or c) one SAE + three AEs. Cross-month metrics are triggers observed across all months in a single community: a) three consecutive AEs, b) consecutive AE and SAE. For final analysis, AE and SAE events and rates per 1,000 will be summarized by wave, RS, and wave by RS. Also, the actual number of opioid-related EMS OD runs and rates per 1,000 will be summarized by wave, RS, and wave by RS.

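### Protocol 8.2 counts only EMS overdose runs with naloxone given, a condition that CTH itself changes, and 8.3.1, 8.3.2 and SAP 6.5 describe the safety count without it

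*Protocol*

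**What the plan says.** **Safety count.** Protocol 8.2 explains that death data arrive six months or more late, so the study uses EMS data as its early warning: "we will monitor emergency medical services (EMS) runs for suspected opioid-related overdoses where naloxone was administered". Protocol 8.3.1 then builds every AE and SAE on EMS data: "The HCS will use EMS opioid-related overdose runs to monitor opioid-related overdose events as an AE and an SAE". Protocol 8.3.2 has the sites report monthly overdose numbers estimated from EMS runs. Neither 8.3.1 nor 8.3.2 mentions naloxone.

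**SAP version.** SAP 6.5 reports that "emergency medical service (EMS) runs for suspected opioid-related OD, as defined by each research site, were monitored as a safety measure". It has no naloxone condition. AEs, SAEs and EMS runs are to be summarised by wave, by site, and by wave within site.

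**What CTH does to naloxone.** Protocol 6.1.1.4, under the first of its three required practices, says that "community action plans will need to include strategies that actively distribute naloxone and provide overdose prevention education to high-risk individuals and their social networks". Optional strategies include "naloxone availability for immediate use in overdose hotspots, and capacity for first responder administration". One of the three secondary hypotheses in Protocol section 3 is "H2: Increase naloxone distribution" in Wave 1 relative to Wave 2.

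**Other EMS measures.** Appendix A lists two separate outcomes from the same state EMS data. Outcome 2.8.1 counts runs involving naloxone; 2.8.2 is "Number of EMS runs for opioid-related incidents or overdoses".

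**The concern.** A safety measure should respond to harm and not to the treatment by some other route. Here the condition that admits a run to the count is the thing CTH sets out to change. Protocol 8.2 does not say who must have given the naloxone, and the difficulty arises on either reading:

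- **The EMS crew must give it.** If a bystander or police officer reverses the overdose first, the crew may give none and the run leaves the count. More community naloxone lowers the count.
- **Any recorded dose qualifies.** Wider supply and more first responders able to administer naloxone bring more runs into the count. It rises with overdoses flat.

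Wave 2 does not receive CTH until July 2022, so the CTH-driven part of any shift falls on one arm during the comparison period. At stake are the early warning itself, the optional Wave 1 versus Wave 2 relatedness comparison in 8.2, and any by-wave harms summary built on the restricted count. The relatedness step begins only after a signal, so it cannot recover a rise that never raised one. The primary endpoint is not affected.

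**Working it through.** The documents give no power or error rate for the safety rule, so there is no planned figure to reproduce. All shares and monthly counts below are assumptions.

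**1. Is there one definition?** Protocol 8.2 takes suspected-overdose runs with naloxone given, giver unstated. Protocol 8.3.1 and 8.3.2 take EMS opioid overdose runs with no naloxone condition. SAP 6.5 takes suspected-overdose runs as each site defines them. A reader cannot tell which count produced the AEs, or whether four sites counted the same thing.

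**2. Effect on a rate comparison.** Let R be the true ratio of overdose rates and S the ratio of the shares of overdoses that end as a counted run. Then observed ratio = R × S, and a true rise disappears when S = 1/R, a relative fall of 1 − 1/R.

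| True rise | Fall in share that hides it | Example from an assumed 70% share |
|---|---|---|
| 20% | 1 − 1/1.20 = 16.7% | 70% to 58% |
| 30% | 1 − 1/1.30 = 23.1% | 70% to 54% |
| 50% | 1 − 1/1.50 = 33.3% | 70% to 47% |

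Conversely, R = 1 with S = 1.25 shows a false 25% rise. Slow drift in S carries fully into a cumulative Wave 1 versus Wave 2 comparison.

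**3. Effect on the monthly AE trigger.** Under 8.3.1 an AE occurs when the month exceeds the mean of the preceding 3 months by more than 3 SD, with the SD taken from the preceding 12 months. Simulating this with independent Poisson counts (200,000 replicates) gives the chance of an AE in one community in one month:

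| Scenario (sudden change in the target month) | Mean 2 runs | 10 | 30 | 100 |
|---|---|---|---|---|
| No change | 0.022 | 0.015 | 0.013 | 0.012 |
| 50% rise, share constant | 0.08 | 0.19 | 0.45 | 0.92 |
| 50% rise, share falls 20% in the same month | 0.04 | 0.05 | 0.10 | 0.25 |
| 50% rise, share falls 33% in the same month | 0.022 | 0.016 | 0.014 | 0.012 |
| Overdoses flat, share rises 50% | 0.08 | 0.19 | 0.45 | 0.92 |

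If the share is already lower throughout the baseline months, the baseline falls too and little is hidden. With a share 17% lower throughout, the chance of an AE for a 20% rise goes from 0.054 to 0.050 at mean 10, from 0.096 to 0.084 at mean 30, and from 0.254 to 0.214 at mean 100. For a 50% rise at mean 30 it goes from 0.449 to 0.385. I re-ran this case and the results agree within simulation error.

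If rise and share both drift in step over 12 months, the chance of any AE in the year at mean 30 is 0.35 for a 50% rise with constant share, 0.17 with the offsetting fall, and 0.15 with no change.

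**4. Reading.** Gradual shifts in naloxone supply act mainly on between-wave comparisons. Full masking of the monthly trigger needs the share to fall in step with the rise.

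**The case against.** The strongest reply is that the naloxone phrase sits only in the narrative of 8.2. The operative definition in 8.3.1, the reporting step in 8.3.2 and the SAP's past-tense account all lack it, so sites may never have applied it. The source cited for the EMS case definition is not reproduced. On this view the problem is one of wording. That stands as a limit on the claim, but it is also half of the point: the documents leave open which count was used.

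Four stronger readings are tempting and are not supported:

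- **That the count is biased toward no signal.** The giver of naloxone is unstated and no shares are printed, so the direction is unknown. Protocol 4.2 also lets Wave 2 adopt new prevention methods with its own resources, so not every shift is confined to Wave 1.
- **That the final harms table is biased.** SAP 6.5 specifies it without the naloxone condition. It inherits the problem only where a site's own definition required naloxone.
- **That a 17% fall in share generally hides a 20% rise.** This holds for a rate comparison. For the monthly trigger it holds only when the fall coincides with the rise.
- **That outcome 2.8.2 is free of the problem.** Its case definition is not printed, and bystander reversal may change whether EMS is called at all.

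There are also backstops. The Steering Committee or DSMB can declare a signal by direction, the DSMB reviews safety and efficacy data by arm at least semi-annually, and there is an unanticipated-problem route. None of these names another timely overdose measure, and SAP 3.5 plans no interim safety analysis.

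**Conclusion.** The concern holds in limited form. As 8.2 is written, the only AE/SAE measure passes through a filter that CTH deliberately alters, so the count can move in Wave 1 without a matching change in overdoses. Separately, 8.2 disagrees with 8.3.1, 8.3.2 and SAP 6.5. The second part is plain from the text. The first is a point of measurement logic whose direction and size the documents do not allow anyone to compute; the figures above rest on assumed shares, assumed monthly means and Poisson variation. No actual masking of harm is shown. This should be corrected because it bears on the credibility of the harms reporting.

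**What to change.** 1. In Protocol 8.2, delete the naloxone condition, which brings it into line with 8.3.1, 8.3.2 and SAP 6.5.
2. In 8.2, 8.3.1 and SAP 6.5, define the AE/SAE series and the harms table as outcome 2.8.2, stating that naloxone administration is not required.
3. Print each site's EMS case definition and hold it constant over the reported period.
4. Tabulate outcome 2.8.1 beside 2.8.2 by wave and site, so that a change in naloxone administration is visible.
5. SAP 6.5 describes the monitoring in the past tense, so past alerts cannot be redefined. Apply items 2 to 4 to the final harms table, and state which definition each site used for the AE/SAE alerts already issued.

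The cost is wording and tabulation, since both outcomes are already listed from the same state EMS data. Two downsides remain: 2.8.2 is somewhat less specific for true opioid overdose, and it is less affected by naloxone supply but not immune to it.

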**Figure 10: Two-Step AE/SAE Review Process**

We consider the following criteria when assessing if an AE or SAE is a safety signal:

- 1) *Has the community had a previous AE/SAE?* This would depict some repeatable pattern within a community rather than one isolated event.
- 2) *Do AEs/SAEs repeat across adjacent months in a community?* Two or more continuous months with an AE/SAE are more indicative of a building concern.
- 3) *Is the observed increase in the number of EMS runs for a month meaningful?* In small communities with low counts of EMS runs per month (often with zero or one EMS run in a month), an increase of a few runs could result in an AE or SAE due to a small 12-

month running standard deviation. Therefore, we only want to flag instances with meaningfully large observed increases.

- 4) *Do several communities have AEs/SAEs in the same month?* We are interested in whether there is a widely prevalent occurrence of AEs/SAEs.

If one or more of these criteria are met for an AE or SAE, and it is thus deemed a safety signal, we will conduct a relatedness analysis which might include examining if there are non-HCS events within a community that might increase opioid related events, if there are state/national events or trends related to increased opioid related events, if HCS and non-HCS populations within each state differ in opioid related events, and if Wave 1 and Wave 2 communities within each state differ in opioid related events. This AE/SAE review process will allow the HCS to use a managed process to determine safety signals and relatedness to the HCS.

## 8.3 Adverse Events

### 8.3.1 Definition of Adverse Events and Serious Adverse Events

The HCS will use EMS opioid-related overdose runs to monitor opioid-related overdose events as an AE and an SAE. These events provide important knowledge about the opioid crisis that the HCS should ethically investigate and report to the community coalitions involved, the National Institute on Drug Abuse (NIDA), the Substance Abuse and Mental Health Services Administration SAMHSA, the Institutional Review Board (IRB), and the Data and Safety Monitoring Board (DSMB). The HCS does not collect any data attributable to specific individuals who received services from the HCS intervention. Only aggregate data for an entire community will be available.

- AEs will be identified by the following criterion:
  - The opioid-related overdose rate for a single month increases **more than three standard deviations** above the moving average of the previous 3 months. For example, the rate in a community for April 2020 is more than three standard deviations greater than the average rate for January, February, and March 2020.
- SAEs will be identified by the following criterion:
  - The opioid-related overdose rate for a single month increases **more than four standard deviations** above the moving average of the previous 3 months. For example, the rate in a community for April 2020 is more than four standard deviations greater than the average rate for January, February, and March 2020.

The standard deviation will be determined as the rolling standard deviation calculated from the 12 months prior to the target month.

Opioid-related overdoses are expected events in the HCS communities because, to be eligible for being selected into the HCS, NIDA required communities to be highly affected by the opioid epidemic with minimum numbers and rates per 100,000 of opioid-related overdose fatalities in 2016.

We will follow a metric-based approach to help identify safety signals and evaluate relatedness to the HCS. Table 11 describes both the monthly and cross-month metrics that serve as triggers

for further analyses. If one of these events occurs, we will consider it a safety signal and will proceed with conducting a relatedness analysis. This analysis will help determine whether observed AE/SAEs are directly related to the HCS intervention and inform further action if necessary.

